#### **8.3.3 Follow-up of AEs and SAEs**

After the initial AE/AESI/SAE report, the Investigator is required to proactively follow each participant at subsequent visits/contacts. At the pre-specified study end-date, all SAEs, and AESIs (as defined in [Section 8.3.8](#)), will be followed until resolution, stabilization, the event is otherwise explained, or the participant is lost to follow-up (as defined in [Section 7.3](#)). Stabilization is

defined as an AE ongoing without any change for at least 3 months. Participants with an AE of Grade >1 will be further followed until the resolution of the AE to Grade 0-1 or starting of a new antineoplastic therapy, whichever occurs first.

Further information on follow-up procedures is provided in Appendix 3 ([Section 10.3](#)).

#### **8.3.4 Regulatory reporting requirements for SAEs**

- Prompt notification by the Investigator to the Sponsor of an SAE is essential so that legal obligations and ethical responsibilities towards the safety of participants and the safety of a study intervention under clinical investigation are met.
- The Sponsor has a legal responsibility to notify both the local regulatory authority and other regulatory agencies about the safety of a study intervention under clinical investigation. The Sponsor will comply with country-specific regulatory requirements relating to safety reporting to the regulatory authority, Institutional Review Boards (IRB)/Independent Ethics Committees (IEC), and Investigators.
- Serious adverse events (SAEs) that are considered expected will be specified in the reference safety information (IB for SAR444245).
  - Investigator safety reports must be prepared for suspected unexpected serious adverse reactions (SUSARs) according to local regulatory requirements and Sponsor policy and forwarded to Investigators as necessary.
- An Investigator who receives an Investigator safety report describing an SAE, SUSAR or any other specific safety information (eg, summary or listing of SAEs) from the Sponsor will review and then file it along with the IB and will notify the IRB/IEC, if appropriate according to local requirements. It is the responsibility of the Sponsor to assess whether an event meets the criteria for a SUSAR, and therefore, should be expedited to regulatory authorities.

#### **8.3.5 Pregnancy**

- Details of all pregnancies in female participants and female partners of male participants will be collected after the start of study intervention and until 60 days (for Cohort B2) or 120 days (for Cohorts A1, A2 and B1) following cessation of study treatment, or 30 days following cessation of study treatment if the participant initiates another anticancer therapy.
- If a pregnancy is reported, the Investigator will record pregnancy information on the appropriate form and submit it to the Sponsor within 24 hours of learning of the female participant or female partner of male participant (after obtaining the necessary signed informed consent from the female partner) pregnancy.
- Abnormal pregnancy outcomes (eg, spontaneous abortion, fetal death, stillbirth, congenital anomalies, ectopic pregnancy) are considered SAEs and will be reported as such.
- The participant/pregnant female partner will be followed to determine the outcome of the pregnancy. The Investigator will collect follow-up information on the participant/pregnant female partner and the neonate, and the information will be forwarded to the Sponsor.

- Any post-study pregnancy-related SAE considered reasonably related to the study intervention by the Investigator will be reported to the Sponsor as described in [Section 8.3.4](#). While the Investigator is not obligated to actively seek this information in former study participants/pregnant female partner, he or she may learn of an SAE through spontaneous reporting.
- Any female participant who becomes pregnant while participating in the study will discontinue study intervention.

### 8.3.6 Cardiovascular and death events

Cardiovascular events that meet AESI criteria should be reported as such (see [Section 8.3.8](#) for details).

### 8.3.7 Disease-related events and/or disease-related outcomes not qualifying as AEs or SAEs

Not applicable.

### 8.3.8 Adverse event of special interest

#### Adverse event of special interest

An adverse event of special interest is an AE (serious or nonserious) of scientific and medical concern specific to the Sponsor's product or program, for which ongoing monitoring and immediate notification by the Investigator to the Sponsor is required. Such events may require further investigation in order to characterize and understand them. Adverse events of special interest may be added, modified or removed during a study by protocol amendment.

The following events need to be reported as AESIs:

- Pregnancy of a female participant entered in a study as well as pregnancy occurring in a female partner of a male participant entered in a study with IMP/NIMP;
    - Pregnancy occurring in a female participant entered in the clinical trial or in a female partner of a male participant entered in the clinical trial. It will be qualified as an SAE only if it fulfills one of the seriousness criteria (see [Section 10.3](#)).
    - In the event of pregnancy in a female participant, IMP should be discontinued.
  - Follow-up of the pregnancy in a female participant or in a female partner of a male participant is mandatory until the outcome has been determined (See [Section 10.4](#)).
- Symptomatic overdose (serious or nonserious) with IMP/NIMP
- An overdose of IMP is defined as: increase of at least 30% of the dose to be administered in the specified duration or if the dose is administered in less than half the recommended duration of administration.
  - An overdose (accidental or intentional) with the NIMP is an event suspected by the Investigator or spontaneously notified by the participant (not based on systematic pills count) and defined as at least twice the intended dose within the intended therapeutic interval, adjusted according to the tested drug.

- An elevated aspartate aminotransferase (AST) or alanine aminotransferase (ALT) lab value that is greater than or equal to 3 times the ULN and an elevated total bilirubin lab value that is greater than or equal to 2 times the ULN and, at the same time, an alkaline phosphatase lab value that is less than 2 times the ULN, as determined by way of protocol-specified laboratory testing or unscheduled laboratory testing\*.

\*Note: These criteria are based upon available regulatory guidance documents. The purpose of the criteria is to specify a threshold of abnormal hepatic tests that may require an additional evaluation for an underlying etiology. The trial site guidance for assessment and follow up of these criteria can be made available. It may also be appropriate to conduct additional evaluation for an underlying etiology in the setting of abnormalities of liver blood tests including AST, ALT, bilirubin, and alkaline phosphatase that do not meet the criteria noted above. In these cases, the decision to proceed with additional evaluation will be made through consultation between the study investigators and the Sponsor.

- Other project-specific AESIs
  - IRR Grade  $\geq 2$
  - CRS Grade  $\geq 2$
  - ICANS of any grade
  - VLS of any grade
  - SARS-CoV-2 infection/COVID-19 disease
  - Any immune-related AE Grade  $\geq 3$
  - Arrhythmia Grade  $\geq 3$

### 8.3.9 Guidelines for reporting product complaints

Any defect in the IMP/NIMP must be reported as soon as possible by the Investigator to the monitoring team that will complete a product complaint form within required timelines.

Appropriate information (eg, samples, labels or documents like pictures or photocopies) related to product identification and to the potential deficiencies may need to be gathered. The Investigator will assess whether or not the quality issue has to be reported together with an AE or SAE.

## 8.4 PHARMACOKINETICS

[figure not shown]
The sampling time-points for PK and ADA for/against SAR444245 and/or other IMPs may be updated during the course of the study based on the updated knowledge of drug behavior upon notification from the Sponsor.

Instructions for the collection and handling of biological samples will be provided by the Sponsor in the laboratory manual. The actual date and time (24-hour clock time) of each sample will be recorded while for samples to be collected at time of biomarker sampling, no specific time on the given day is necessary.

[figure not shown]
Instructions on the collection, processing, storage, and shipment of samples will be provided in the laboratory manual. Sample analysis will be performed at a laboratory designated by the Sponsor.

Samples collected for analyses of SAR444245 concentration may also be used to evaluate safety or efficacy aspects related to concerns arising during or after the study and any remaining plasma/serum volume may also be used for further exploratory analysis if deemed relevant.

## 8.5 GENETICS AND/OR PHARMACOGENOMICS

[figure not shown]

## 8.6 BIOMARKERS

## 8.9 USE OF BIOLOGICAL SAMPLES AND DATA FOR FUTURE RESEARCH

## 9 STATISTICAL CONSIDERATIONS

Please refer to substudies protocols for additional statistical considerations.

### 9.1 STATISTICAL HYPOTHESES

All cohorts of the study are designed to obtain antitumor activity, safety, PK, and PDy data on SAR444245 administered in combination with other anticancer therapies.

The study is designed to assess the clinical benefit of SAR444245 with other anticancer therapies in participants with HNSCC. As this study is not intended to explicitly test a hypothesis, calculations of power and Type I error were not considered in the study design. No formal testing procedure is planned.

### 9.2 SAMPLE SIZE DETERMINATION

Overall, in the core phase, the plan is to treat approximately 40 participants per cohort.

#### Core Phase

Table 5 lists estimated ORR and the corresponding 90% exact CIs by number of responders in each cohort.

**Table 5 - Estimated objective response rate (ORR) and 90% CI for core phase**

| Number of responders
(N=40) | ORR   | 90% CI for ORR
(Clopper-Pearson) |
|--------------------------------|-------|-------------------------------------|
| 6                              | 15.0% | (6.7%, 27.5%)                       |
| 7                              | 17.5% | (8.5%, 30.4%)                       |
| 8                              | 20.0% | (10.4%, 33.2%)                      |
| 9                              | 22.5% | (12.3%, 36.0%)                      |
| 10                             | 25.0% | (14.2%, 38.7%)                      |
| 11                             | 27.5% | (16.3%, 41.4%)                      |
| 13                             | 32.5% | (20.4%, 46.6%)                      |
| 15                             | 37.5% | (24.7%, 51.7%)                      |
| 17                             | 42.5% | (29.2%, 56.7%)                      |
| 19                             | 47.5% | (33.8%, 61.5%)                      |
| 24                             | 60.0% | (45.8%, 73.1%)                      |

With a sample size of 40 study participants in each cohort in the core phase, the probability of observing 1 or more instances of a specific AE with a true incidence rate of 1%, 2%, or 5% is 33.1%, 55.4%, or 87.1%, respectively. This provides reasonable assurance that events occurring at  $\geq 5\%$  frequency can be identified in this study.

### 9.3 POPULATIONS FOR ANALYSES

The following populations for analyses are defined:

**Table 6 - Populations for analyses**

| Population | Description   |
|------------|---|
| Exposed    | Exposed population will include all participants who have given their informed consent and received at least one dose (even incomplete) of IMP (SAR444245 or other anticancer therapies). |
| Efficacy   | Efficacy population will include all participants from the exposed population with at least one evaluable post-baseline tumor assessment or who permanently discontinued study treatment. |
| PK         | The PK population will include all participants from the exposed population with at least 1 PK concentration available after the first dose of study intervention.                        |
| PDy        | The PDy population will include all participants from the exposed population with at least 1 PDy parameter assessed after the first dose of study intervention.                           |

### 9.4 STATISTICAL ANALYSES

The statistical analysis plan (SAP) will include a more technical and detailed description of the statistical analyses described in this section. This section is a summary of the planned statistical analyses of the most important endpoints including primary, key secondary endpoints and exploratory endpoints.

#### 9.4.1 General considerations

This study is not intended to explicitly test a hypothesis, and 90% CI will be provided for primary and secondary efficacy endpoints for descriptive purpose only.

All efficacy analyses will be performed on the efficacy population and analyzed by cohort. Some cross-cohort summaries will be presented too. Results will be presented by core phase and overall phase (combining core phase and expansion phase, if expansion phase applies). Objective response rate, as well as PFS, DOR, and CBR will be derived using the local radiologist's/Investigator's assessment for all cohorts. Central imaging may be done retrospectively if significant activity is observed. The assessments for all cohorts will use RECIST 1.1.

All safety analyses will be performed on the exposed population by cohort, by dose (if applicable), and overall (if applicable). Baseline value will be defined as the latest value or measurement taken up to the first administration of the IMP.

The analysis period will be divided into 3 segments:

- The pre-treatment period is defined as the time from when the participants give informed consent to the first administration of the IMP.
- The on-treatment period (ie, treatment-emergent period) is defined as the time from the first administration of IMP up to 30 days after the last administration of IMP.

- The post-treatment period is defined as the time from the 31 days after the last administration of IMP.

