## 4 STUDY DESIGN

### 4.1 OVERALL DESIGN

This is a Phase 2, multi-cohort, un-controlled, non-randomized, open-label, multi-center study assessing the antitumor activity and safety of SAR444245 combined with other anticancer therapies in participants with HNSCC.

This study is developed as a master protocol in order to accelerate the investigation of SAR444245 in combination with various anticancer therapies by identifying early signals. This design is with the flexibility to open new treatment cohorts as new treatment combinations become available and close existing treatment arms that demonstrate minimal clinical activity or unacceptable toxicity.

The information that is introductory and common to all cohorts is included in the present document (“Master Protocol”), and cohort-specific elements are included in separate substudies. This study is designed with the flexibility to open new treatment arms or add new indications as permitted by scientific rationale.

The study consists of a core phase for all cohorts, with a safety run-in and an expansion phase for specific cohorts (see [Figure 1](#)). The results of an interim analysis after the core phase will decide if the expansion phase will be opened. Further details on study design are provided in each substudy. An overview of the study intervention and disease being treated for each cohort is provided in [Table 3](#).

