#### **9.4.2 Primary endpoint(s)**

The BOR is the best overall response observed from the date of first IMP until disease progression, death, cut-off date or initiation of post-treatment anti-cancer therapy, whichever occurs first. The BOR will be summarized with descriptive statistics. The ORR is the primary endpoint defined as the percentage of participants from the analysis population with BOR is either CR or PR, assessed per Investigator. The ORR and the corresponding 90% confidence intervals calculated from Clopper-Pearson exact method will be also presented. All objective responses need to be confirmed by a subsequent assessment performed at least 4 weeks apart from the initial response observation.

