## 9.5 INTERIM ANALYSES

During the core phase, no formal interim analyses are planned. However, the cumulative safety data for each study intervention across cohorts will be reviewed periodically by the Data Monitoring Committee (DMC). The enrollment will not be paused or stopped during the safety monitoring unless severe safety concern arises.

In addition, in order to support project strategic planning and design of future studies, informal interim analysis(es) may be conducted during the study, eg, in each cohort, after 20 participants have undergone two post-baseline tumor assessments (approximately 18 weeks from the 20 participants are first treated) or have discontinued study treatment whichever is earlier.

For each cohort, the cut-off date for the final analysis will be 3 years from cohort last patient-in (LPI).

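### In a cohort that expands because of its core-phase response, both planned ORR presentations (core, and core plus expansion) are biased upward; expansion-alone ORR should be added.

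*Protocol*

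**What the plan says.** Master protocol Section 4.1 (and the Synopsis) makes expansion depend on core data: "The results of an interim analysis after the core phase will decide if the expansion phase will be opened". Section 9.4.1 fixes two presentations of the results: "Results will be presented by core phase and overall phase (combining core phase and expansion phase, if expansion phase applies"). Expansion participants alone are not one of them. For the primary endpoint, Section 9.4.2 names one interval: "The ORR and the corresponding 90% confidence intervals calculated from Clopper-Pearson exact method will be also presented". No adjustment for the opening decision is mentioned.

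Section 9.5 says "During the core phase, no formal interim analyses are planned". It then describes periodic safety review by the data monitoring committee, optional informal looks (for example after 20 participants) and the final cut-off. The post-core analysis that decides on expansion is not listed there.

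On size, Section 9.2 says "Overall, in the core phase, the plan is to treat approximately 40 participants per cohort". No expansion size and no opening threshold appear in the master protocol or in Substudy 01. The role of the intervals is limited: Section 9.4.1 says "90% CI will be provided for primary and secondary efficacy endpoints for descriptive purpose only", and Section 9.1 says that "calculations of power and Type I error were not considered in the study design".

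**The concern.** An overall-phase ORR exists only for cohorts whose core result was good enough to continue. If response drove that decision, the core count in those cohorts comes from the upper part of its distribution. Adding expansion participants dilutes the excess but does not remove it, and the ordinary interval treats the total as one sample of fixed size. The core-phase ORR of an expanded cohort carries the same excess undiluted. The one estimate free of this selection, from the expansion participants alone, is not among the planned presentations.

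The excess is largest when the combination adds little to the historical response rate. Section 4.2 says the cohorts will be judged against historical data for the partner agents, so this is the case in which a reader most needs an undistorted figure.

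**Working it through.** **The plan's own figures first.** Clopper-Pearson limits for x responders of n at 90% are the 5% quantile of Beta(x, n−x+1) and the 95% quantile of Beta(x+1, n−x). With n = 40 this reproduces all 11 rows of Table 5 (Section 9.2), for example 10/40: 14.2% to 38.7%.

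**Inputs from the documents**
- Core size 40 (Section 9.2).
- 90% Clopper-Pearson interval (Section 9.4.2).
- True ORR of 19%: the first-line pembrolizumab monotherapy figure for CPS ≥1 (Substudy 01, Section 2.2.3.1).
- True ORR of 15%: the top of the 10%–15% second-line range (master protocol, Section 2.1).

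**Assumptions, not in the available text**
- Expansion size n2 = 40 (20 and 60 also tried).
- Expansion opens if core responders X1 ≥ r, with r = 8 or 10 (12 and 13 also tried).
- A true ORR of 25% as a case of moderate benefit.

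**Model.** X1 ~ Bin(40, p) and X2 ~ Bin(n2, p), independent. Given opening:
- core mean = E[X1 | X1 ≥ r] / 40
- pooled mean = (E[X1 | X1 ≥ r] + n2·p) / (40 + n2)
- expansion-alone mean = p, because X2 does not depend on X1
- pooled coverage = P(the interval for X1 + X2 of 40 + n2 contains p | X1 ≥ r)

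**Results with n2 = 40**

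| r | True ORR | P(opens) | E[X1 given opening] | Core bias | Pooled mean | Pooled bias | Totals of 80 whose interval contains the truth | Coverage |
|---|---|---|---|---|---|---|---|---|
| 10 | 19% | 22% | 11.09 | +8.7 | (11.09 + 7.6)/80 = 23.4% | +4.4 | 10 to 21 | 84.4% |
| 10 | 25% | 56% | 11.93 | +4.8 | (11.93 + 10)/80 = 27.4% | +2.4 | 14 to 26 | 91.1% |
| 8 | 15% | 24% | 9.03 | +7.6 | (9.03 + 6)/80 = 18.8% | +3.8 | 7 to 17 | 83.4% |

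Biases are in percentage points. With equal phase sizes the pooled bias is half the core bias. In the first row the lower limit lies above the true ORR in 15.6% of expansions, against 4.1% for an unselected sample of 80 (nominal 5%).

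**Across the grid** (n2 = 20, 40, 60; r = 8, 10, 12, 13; true ORR 15% to 35%): pooled bias given opening is upward in every cell, from +0.1 to +12.4 points. Coverage is below 90% in every cell where expansion opens 28.5% of the time or less, and at least 91.1% in every cell where it opens 42% of the time or more.

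**Averaged over all outcomes**, with the core result reported when a cohort does not expand, bias is slightly downward (0 to −1.7 points) and coverage is 89.9% to 95.9%.

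**The case against.** Five arguments on the other side deserve weight.

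- **The rule may exist elsewhere.** The master protocol refers to the substudies for design details and further statistics. Substudy 01 is core-only (its Section 4.2), Substudy 02 is available only up to its table of contents, and Substudies 04 and 05 are not available. A reader might infer that no opening rule exists; the documents do not support that. One can say only that the master protocol and Substudy 01 give none.
- **The interval is not generally too short.** A reader might infer that it always under-covers. It does not: Clopper-Pearson conservatism keeps coverage at 91% or more when the true ORR is near or above the threshold. Much worse figures can be produced, such as 55% coverage at a true ORR of 19% with opening at 13 of 40, but expansion then opens only 3% of the time.
- **The decision may not rest on response alone.** The schema notes (Section 1.2) give expansion a safety purpose as well as an activity one. A softer rule selects less sharply. This stands, and limits what any figure here can claim.
- **The results are descriptive, and the SAP may add detail.** Both are true, and nothing in the protocol ranks the overall-phase ORR above the core one. But absence of a test does not remove bias, and Section 9.4.1 itself fixes which results are shown.
- **Core is reported separately, and expansion can be obtained by subtraction.** The core figure does not help, because given opening it is more biased than the pooled one. Subtraction recovers the expansion counts, but the reader has to know to do it and must compute the interval.

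Nor does Section 9.5 contradict Section 4.1: no formal interim during the core phase is compatible with one after it. The deciding analysis is simply missing from the section where it belongs.

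**Conclusion.** The point holds in a conditional form. In any cohort that expands on response, both planned ORR presentations are biased upward, and the ordinary 90% interval on the pooled ORR can under-cover when the true ORR is clearly below the opening threshold. Plausible sizes are 2 to 4 points of pooled bias, with coverage from about 83% to 91%. These rest on an assumed expansion of 40, an assumed opening at 8 or 10 of 40, and a decision driven by the responder count. The direction of the bias needs only that higher core response makes opening more likely. Cohort A1 is unaffected. The upward bias applies to cohorts that expanded, not to the average over all cohorts, but expanded cohorts are the only ones that will have an overall-phase ORR.

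**What to change.** In Section 9.4.1, add for any expanded cohort the expansion-phase-alone ORR with its own 90% Clopper-Pearson interval, and label the overall-phase ORR and interval as unadjusted for selection on the core result. The expansion-alone estimate has no bias from this selection and coverage of at least 90% by construction, and it needs no opening rule to compute.

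In Section 9.5, list the post-core analysis and cross-reference its opening criterion, in the substudy or wherever it is held. A two-stage-adjusted pooled estimate is optional: it would need a binding numerical rule, which is a real trade-off in a flexible signal-finding study.

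The cost is one extra table row and a few sentences, with no extra participants. The added interval is wider: at 25% observed, 10/40 gives 14.2% to 38.7% (24.5 points), while 20/80 by the same formula gives 17.2% to 34.2% (17.0 points).
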